11.3.8. Reporting of Adverse Events

Every SAE occurring throughout the trial must be reported by telephone, email or fax to the sponsor, LSM and DSMB by the investigator as soon as (s)he is alerted of it and within one working day, even if the investigator considers that the adverse event is not related to vaccination. The investigator will then complete a SAE report form as soon as possible and within five working days or seven calendar days.

Any relevant information concerning the adverse event that becomes available after the SAE report form has been sent (outcome, precise description of medical history, results of the investigation, copy of hospitalisation report, etc.) will be forwarded to the Sponsor in a timely manner. The anonymity of the subjects shall be respected when forwarding this information.

SAEs that are suspected to be related to the vaccine will be reported to the Ethics Committee within 15 calendar days of the site becoming aware of the event. If the event is fatal or life-threatening, the event will be reported within 7 calendar days.

Suspected unexpected serious adverse reactions (SUSARs) will be reported according to national regulatory guidelines. The sponsor pledges to inform the Authorities of any trial discontinuation and specify the reason for discontinuation.

The causal relationship between the AE and the product will first be evaluated by the investigator with the following scale:

No relationship: No temporal relationship to study product; and Alternate aetiology (clinical state, environmental or other interventions); and Does not follow known pattern of response to study product

Possible relationship: Reasonable temporal relationship to study product; or Event not readily produced by clinical state, environmental or other interventions; or Similar pattern of response to that seen with other vaccines

Probable relationship: Reasonable temporal relationship to study product; and Event not readily produced by clinical state, environment, or other interventions or Known pattern of response seen with other vaccines

Definite relationship: Reasonable temporal relationship to study product; and Event not readily produced by clinical state, environment, or other interventions; and Known pattern of response seen with other vaccines

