Similar mild 'flu-like symptoms can occur with AdCh63 ME-TRAP. These symptoms occur in 28/39 of volunteers at 5 x 10^{10} vp intramuscularly. The frequency of 'flu-like symptoms increases with use of the 2 x 10^{11} vp dose to 9/10. Objective fever has not been observed in 46 males in Africa, and has occurred in 26/85 volunteers in the UK (at doses up to 2 x 10^{11} vp).

HDCRV

Mild systemic reactions such as fever, headache, dizziness and gastrointestinal symptoms occur in 5–40%, and systemic hypersensitivity following booster injections in 6% of vaccinees, but are less common following primary immunization.

With any vaccine, serious allergic reactions including anaphylaxis may occur. The exact risk of anaphylaxis is difficult to quantify, and is estimated at approximately 1 in 10^5 to 10^6 . Volunteers will be vaccinated in a clinical area where Advanced Life Support drugs and equipment are immediately available for the management of serious adverse reactions.

Prophylactic use of paracetamol or non-steroidal anti-inflammatory drugs is not required. Parents of study subjects will be provided with paracetamol and they will be advised to use this drug to treat local or systemic adverse events as they see fit should these develop post-immunisation, but not prophylactically.

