4.3. Endpoints

4.3.1. Primary Endpoint

All solicited and unsolicited local and general vaccine-linked adverse events (AEs) including clinically significant laboratory abnormalities.

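### The causality scale judges an event's pattern against the study product in one grade and against other vaccines in the other three, leaving one overlap and one gap at the related/unrelated line

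*Protocol*

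**What the plan says.** Section 11.3.8 has the investigator make the first causality assessment on a four-grade scale.

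- *No relationship* needs three things together: "No relationship: No temporal relationship to study product", then "Alternate aetiology (clinical state, environmental or other interventions"), and finally that the event "Does not follow known pattern of response to study product".
- *Possible* needs any one of three: "Possible relationship: Reasonable temporal relationship to study product", or an event not readily produced by other causes, or "Similar pattern of response to that seen with other vaccines".
- *Probable* needs reasonable timing and then "Event not readily produced by clinical state, environment, or other interventions or Known pattern of response seen with other vaccines".
- *Definite* needs all three: timing, no ready alternative explanation, and the pattern known from other vaccines.

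The section gives no rule for an event that satisfies more than one grade, or none.

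Relatedness is used elsewhere. The primary endpoint in 4.3.1 is "All solicited and unsolicited local and general vaccine-linked adverse events (AEs) including clinically significant laboratory abnormalities". Section 11.3.7 follows persisting events to resolution or stabilisation if they are graded possible, probable or definite. Section 11.3.8 sends serious events suspected to be vaccine-related to the Ethics Committee within 15 calendar days, or 7 if fatal or life-threatening. Section 11.3.6 treats every local reaction as causally related. Section 7 leaves investigators unblinded in Groups 2 and 3.

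**The concern.** A causality scale should give every event exactly one place, and its lowest grade should be the negation of the grade above it. Here two of the three criteria, timing and alternate cause, do reverse cleanly between *No relationship* and *Possible*. The third does not, because its point of reference moves from the study product to other vaccines. No related grade mentions the study product's own pattern at all.

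Two assessors who both apply the text correctly could therefore put one event on opposite sides of related/unrelated, or find no grade for it. In Groups 2 and 3 that discretion falls to an investigator who knows the allocation. Section 4.1 expects much concurrent illness in these children, so events with another cause and weak timing will need grading.

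**Working it through.** The scale is a set of logical rules and the protocol states no figure to reproduce, so the check is an enumeration.

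**Inputs (all from 11.3.8).** Four yes/no facts about an event:

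- T: reasonable temporal relationship
- A: alternate cause present
- Ks: follows the known pattern of the study product
- Ko: follows a pattern seen with other vaccines

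This gives 2 × 2 × 2 × 2 = 16 combinations. Two simplifications are made: an event not readily produced by other causes is taken as not A, and the similar pattern in *Possible* is treated as the known pattern in *Probable* and *Definite*.

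**Rules as written.**

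- No relationship = not T and A and not Ks
- Possible = T or not A or Ko
- Probable, reading 1 = T and (not A or Ko)
- Probable, reading 2 = (T and not A) or Ko
- Definite = T and not A and Ko

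**Step 1, the boundary.** *No relationship* fixes three facts and leaves Ko free, so it covers 2 combinations. *Possible* fails only when not T, A and not Ko, which leaves Ks free, so it fails in 2 and covers 16 − 2 = 14. The total 2 + 14 = 16 looks complete, but it hides one overlap and one gap:

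| T | A | Ks | Ko | Grades met |
|---|---|---|---|---|
| no | yes | no | yes | No relationship and Possible (also Probable under reading 2) |
| no | yes | yes | no | none |

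**Step 2, reactions known for the product only (Ks yes, Ko no).** The results are the same under both readings of *Probable*. The last column applies the change given under the fix.

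| T | A | Highest grade as written | After the fix |
|---|---|---|---|
| yes | no | Probable | Definite |
| yes | yes | Possible | Probable |
| no | no | Possible | Possible |
| no | yes | none | Possible |

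**Step 3, the wording of Probable.** The two readings differ only when T is no and Ko is yes, with A and Ks free: 4 combinations. One is the overlap in Step 1. The other three meet *Possible* and not *No relationship* under either reading, so they count as related whichever is used.

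**Step 4, one pattern criterion.** Let K = Ks or Ko. Then No relationship = not T and A and not K, and Possible = T or not A or K, its exact complement. The counts become 1 and 15, with no overlap and no gap. With *Probable* bracketed as in reading 1, *Definite* lies inside *Probable* and *Probable* inside *Possible*, so the scale is ordered.

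**The case against.** The strongest reply is that the two faulty combinations will be rare. Both need no temporal link and an alternate cause, yet a match to a vaccine's pattern of response. Timing is itself part of the patterns described in 2.3.1 (flu-like illness within 24 hours, local reactions resolving within 48 hours), so the four facts are not independent and a share of 16 combinations says nothing about frequency. This stands.

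Safeguards also stand. Every serious event goes to the sponsor, the local safety monitor and the DSMB whatever its grade, local reactions are related by rule, and 11.3.6 collects event details regardless of relationship. Section 11.3.3 treats a relationship that cannot be ruled out as an adverse reaction, which points doubtful cases towards related. But that definition assigns no grade, and a sensible habit of taking the higher grade is not written down and would not place the ungraded case.

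On *Probable*, the punctuation favours reading 1: the first connective follows a semicolon and the second does not. Brackets are a tidy-up.

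Three stronger readings are tempting and not supported:

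- A reader might infer that reactions specific to these vectors can never be *Definite*. Sections 2.1 and 2.3.1 describe other vaccines on the AdCh63 and MVA vectors, and these may supply the required pattern. Only a reaction known for this product and for no other vaccine is held back.
- A reader might infer that late gastrointestinal illness in children falls in the overlap, because for the rabies vaccine 2.3.1 says "Mild systemic reactions such as fever, headache, dizziness and gastrointestinal symptoms occur". Sharing a symptom name is not matching a pattern of response. Vomiting is itself solicited in children under 11.2, and no rate is given from which to count children affected.
- A reader might extend that example to dose escalation. Section 12.4.1 does review relationship to vaccination, but the paediatric stages in 4.4.1 rest on 14-day safety profiles, and an illness later than that is outside them.

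**Conclusion.** The inconsistency is real and is in the stated rule; it is not a detail left for later. As written, one combination is both unrelated and possibly related, one has no grade, and a timely, unexplained reaction known only for the study product stops at *Probable*. The first two lie on the related/unrelated boundary. The third does not affect whether an event counts: 11.3.7 treats the three related grades alike, and no rule in the protocol turns on *Definite* against *Probable*.

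The exposure is limited to general and laboratory events, and the number affected is probably small and cannot be estimated from the document. The conclusion rests on two assumptions: that the criteria can be read as yes/no facts, and that the vaccine-linked events of 4.3.1 and the suspected-related events of 11.3.8 are those graded *Possible* or above, which the protocol implies but does not say. The correction is worth making because the primary endpoint depends on relatedness, the grader is unblinded in the children's groups, and the change is slight.

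**What to change.** In 11.3.8:

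1. Use one pattern criterion in all four grades: *known pattern of response to the study product or to other vaccines*, negated in *No relationship*. This makes *No relationship* the exact complement of *Possible*.
2. Write *Probable* as: temporal relationship AND (not readily explained by other causes OR known pattern).
3. State that the highest grade met applies.

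This resolves both boundary cases as *Possible*, in line with 11.3.3. Referring to the study product alone in all four grades would also remove the overlap and the gap, but would place the overlap case under *No relationship*.

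The cost is a few words in 11.3.8 and in the CRF key, and a quick re-check of general and laboratory events already graded in Group 1. No dose, schedule or clinical rule changes.

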11.3.9. Pregnancy

Not applicable.

12. STATISTICS

12.1. Study Design and Hypothesis

This is an single blinded controlled phase I dose-escalation safety study. As this is a descriptive study to acquire safety data in a small group of volunteers, null hypotheses are not relevant.

The study design will allow a comparison between safety and tolerability of two doses of AdCh63 ME-TRAP. The secondary objective is to obtain immunogenicity data on the use of these vaccines. This may be used to compare the immunogenicity of two doses of AdCh63 ME-TRAP.

It will also allow a comparison between the safety and tolerability of two doses of MVA ME-TRAP in children, although this is a tertiary endpoint.

12.2. Study Population

We will enrol 16 healthy male volunteers between the ages of 18 and 50 years, 6 in group 1A and 10 in group 1B. We will enrol 6 healthy children aged between 2 and 6 years in each of the following groups; 2A, 2B, 2C, 3A, 3B and 3C. It is anticipated that most volunteers will be recruited from the region served by Sukuta Health Centre.

12.3. Sample Size Considerations

The sample size for phase I studies balances the need to avoid exposing a large group to an unknown risk with the need for data on an adequate sample. The aim is not to provide pre-marketing safety data, but to justify the future study of larger groups.

12.4. Planned Interim Analysis

12.4.1. Safety Review

Group 1:

The frequency, intensity and relationship to vaccination of solicited and unsolicited adverse events with a dose of 1 x 10^{10} vp AdCh63 ME-TRAP in adults (Group 1A) will be reviewed by the LSM prior to dose escalation to 5 x 10^{10} vp (Group 1B).

Groups 2 & 3:

VAC 041 Protocol: Version 6.0

The frequency, intensity and relationship to vaccination of solicited and unsolicited adverse events will be reviewed as outlined in section 4.4.1.

12.4.2. Immunogenicity or Efficacy Review

No interim immunogenicity analysis is planned.

12.5. Final Analysis Plan

No formal statistical analysis is planned for this study.

13. DATA HANDLING AND RECORD KEEPING

13.1. Data Management

The Principal Investigator will be responsible for receiving, entering, cleaning, querying, analysing and storing all data that accrues from the study. Responsibility for this may be delegated to the data manager at MRC. The data will be entered into the subjects' CRFs. Data will be subsequently transferred to an electronic database for analysis.

If any changes to the protocol are necessary during the study a formal amendment will be presented to the sponsor prior to submission to the relevant ethical and regulatory agencies for approval unless to eliminate an immediate hazard(s) to study participant without prior ethics approval. Any unforeseen and unavoidable deviations from the protocol will be documented and filed in as a protocol deviation in the Trial Master File, with explanation.

13.2. Data Capture Methods

Data capture will be on paper CRFs. The CRFs will be considered source documents as healthy volunteers will not have hospital case-notes.

Adverse events will be tabulated in an electronic database (OpenClinica®) for descriptive analysis.

Immunological data will be transferred to an electronic database for analysis without any volunteer identifier apart from the unique volunteer number.

13.3. Types of Data

Data collected will include solicited and non-solicited adverse event data, concomitant medications, clinical laboratory and exploratory immunology data. Source documents will include laboratory results and the case record file containing the case report forms for each volunteer as the healthy volunteers participating in this study may not have medical notes.

13.4. Timing/Reports

Annual Safety Report: Due on anniversary of Regulatory Approval – sent to Regulatory and Ethical Bodies Annual Progress Report: Due on anniversary of Ethical Approval – sent to Ethics Committee

13.5. Archiving

The investigator must keep all trial documents for at least 15 years after the completion or discontinuation of the trial, whatever the nature of the investigational centre (private practice, hospital, institution).

VAC 041 Protocol: Version 6.0

13.6. *Protocol Deviations*

Any unforeseen and unavoidable deviations from the protocol will be documented and filed in a protocol deviation folder, with explanation.

14. DATA ACCESS AND QUALITY ASSURANCE

14.1. Direct Access to Source Data/Documents

The principal investigator will provide direct access to the source data documents to the Ethics Committee, to the regulatory agency, and to authorised representatives of the sponsor, permitting trial-related monitoring and audits.

14.2. Quality Assurance

14.2.1. Modifications to the Protocol

Any amendments to the trial that appear necessary during the course of the trial must be discussed by the investigator and sponsor concurrently unless to eliminate an immediate hazard(s) to study participants. If agreement is reached concerning the need for an amendment, it will be produced in writing by the sponsor and/or the investigator and will be made a formal part of the protocol. An amendment requires Ethics Committee approval.

All amendments must also be transmitted to Regulatory Authorities, if applicable.

An administrative change to the protocol is one that modifies administrative and logistical aspects of a protocol but does not affect the subjects' safety, the objectives of the trial and its progress. An administrative change does not require Ethics Committee approval. However, the Ethics committee must be notified whenever an administrative change is made.

The investigator is responsible for insuring that changes to an approved trial, during the period for which Ethics Committee approval has already been given, are not initiated without Ethics Committee review and approval except to eliminate apparent immediate hazards to the subject.

14.3. Monitoring

14.3.1. Initiation Visit

An initiation visit will be performed before the inclusion of the first subject in the study. The Monitor will verify and document that the material to be used during the trial has been received and that the investigational team has been properly informed about the trial and regulatory requirements.

14.3.2. Follow-Up Visits

The Monitor will carry out regular follow-up visits. The investigator commits to being available for these visits and to allow the monitoring staff direct access to subject medical files, if existing, and CRFs. The Monitor is committed to professional secrecy.

During the visits, the Monitor may:

- Carry out a quality control of trial progress: in respect of protocol and operating guidelines, data collection, signature of consent forms, completion of documents, SAE, sample and product management, cold chain monitoring
- Inspect the CRFs, TMF and correspondent correction sheets

The Monitor will discuss any problem with the investigator and define with him the actions to be taken.

14.3.3. Close-out Visit

A close-out visit will be performed at the end of the trial. Its goals are to make sure that:

- The centre has all the documents necessary for archiving
- All unused material has been recovered
- All vaccines have been accounted for

15. FINANCE

Justification of the Budget

The resources requested are for the proper conduct of the phase I trials and related activities in The Gambia. All salaries are based on MRC Laboratories, Gambia pay scales. A study physician is needed to conduct the trial under the supervision of the PI and [name]. 3 nurses/field workers are needed to help with the recruitment, follow-up and provide nursing care for the study subjects. Three laboratory assistants are needed to provide laboratory support for the study. A full time driver is needed to help with transportation of staff and study subjects for the duration of the study. A project manager is needed to ensure that all procedures and their documentation meet GCP and GCLP quality standards.

16. ETHICAL CONSIDERATIONS

16.1. Good Clinical Practice

This trial will be conducted in accordance with the Declaration of Helsinki as agreed by the World Medical Association General Assembly (Seoul 2008), ICH Good Clinical Practice and local regulatory requirements.

16.2. Ethical Review

Before the inclusion of the first subject in the study, the protocol must be approved by Ethical Review Committees in The Gambia and Oxford (OXTREC).

16.3. Informed Consent

The volunteer should give written informed consent before being included in the trial, after having been informed of the nature of the trial, the potential risks and their obligations. Informed consent forms will be provided in duplicate (original kept by the investigator, one copy kept by the subject or the subject's legally acceptable representative).

Please refer to Section 9.1 for a detailed discussion of the informed consent process.

16.4. Special Considerations

Potential subjects with HIV

VAC 041 Protocol: Version 6.0

Although it is standard practice to obtain safety data in healthy subjects before immunising those with HIV, we do not believe the vaccine to be unsafe in HIV. The need for an HIV test before immunisation would preclude widespread delivery of a successful immunisation, and it is clearly desirable to protect HIV infected individuals as well as uninfected. These highly attenuated vectors are unable to replicate in human cells, and are very likely to be safe in HIV. MVA vectored vaccines have been used safely in volunteers with HIV infection in small studies, and adults infected with HIV have previously received MVA ME-TRAP. In the current protocol HIV infection will be an exclusion criterion.

Confidentiality

All HIV tests will be identified by a unique code number only. The code key will be kept by the principal investigator who will be responsible for holding these files securely.

All other blood results and adverse event data will be encoded in an electronic database and stored securely by the principal investigator.

Maintaining confidentiality

A potential danger of excluding volunteers who are HIV positive is that excluded volunteers will be presumed to be HIV positive. We therefore propose to over recruit in this study and have stipulated other exclusion criteria. It would therefore not be a foregone conclusion that any excluded volunteer would be HIV positive, and this will be explicit in community and individual discussions. This approach has been used successfully previously, and we believe has protected the confidentiality of those screening positive. Only the principal investigator and a designee, if applicable, will be able to link HIV test results for the study population to individuals.

Inducement

There may be a perception amongst volunteers of benefit from physical examination, laboratory screening and HIV testing in the current study, in addition to free health care provided during the study period for non-vaccine related medical problems. We will also offer compensation for transport expenses for all study subjects, and time away from work or duties at home for adults study subjects in order to attend for immunisation and follow-up.

We do not feel these benefits are excessive, and believe it would be unreasonable to request the cooperation of a population in regular employment or with childcare responsibilities without offering compensation for time.

The use of a licensed vaccine in this trial may be considered to provide advantage to the control group over the vaccine group; therefore all volunteers in groups 2 and 3 will be offered a standard course of rabies vaccine at the end of the trial. This will be arranged by [name] but will not be considered part of this trial.

